3.3.5 Randomization

Randomization of study patients will be done in equal proportion to Arm I (SIMRT) and Arm II (HTIMRT) using a permuted block design stratified by baseline PSA (<10 v 10 to ≤100), Gleason score (6-7 v 8-10), and short term androgen deprivation therapy (Y v N). The pre-study Gleason score, not that determined by post-MRI biopsy will be used in determining a patient's

stratum; however, patients will not be randomized until after the fiducial markers and prostate biopsies (if elected by the patient) have been performed. Patients whose Gleason score comes back higher and in whom the use or length of androgen deprivation becomes an issue, will then have the opportunity to withdraw from the study without creating potential imbalances. The ability for the patients to withdraw at any time will be described from outset. Based on prior experience, the proportion of patients that withdraw before treatment is about 1-2%. In this trial, the potential for withdrawal is estimated to be 2-3 times higher because of anticipated upgrading (higher Gleason scores in the post MRI biopsies).

Randomization lists for each stratum will be prepared by SCCC Biostatistics prior to the first patient enrollment and provided to the SCCC CRS office where they will be maintained independent of the study team. Members of the study team, including those responsible for patient enrollment, will not have access to the randomization lists.

After informed consent is signed; eligibility is confirmed, a determination has been made regarding optional STAD, the fiducial markers placed and, if elected, prostate biopsies performed, a member of the study team will randomize the subject as per CRS guidelines. The randomization should occur within two weeks after the fiducial marker placement, if applicable or after enrollment.

The nature of study treatment (40 SIMRT vs. 38 HTIMRT treatments) requires that the patients know their treatment. With respect to the collection, processing and analysis of study data, including that deriving from tissue and blood samples, only published data will be available to the patients.

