14.2 Sample size, accrual rate and study duration

Study size is based on our primary objective of demonstrating that, compared to SIMRT, HTIMRT reduces the two year post treatment failure rate, by which we mean the proportion of patients with either biopsy failure or earlier evidence (within two years of treatment completion) of biochemical and/or clinical failure. (See definition in Section 9.1.) We expect the two-year failure rate in the standard fractionation arm to be 52.5%, representing the combined effect of a small rate of biochemical or clinical failure within two years, approximately 5%, and a relatively high rate of positive biopsy among the remaining 95% of patients, namely 50% ($0.05 + 0.95 \times 0.50 = 0.525$). This estimate is based on prior findings on randomized trials previously

organized by the PI. (75) Assuming equal allocation of patients to SIMRT and HTIMRT and sufficient follow-up to determine failure status at two years, a study size of 36 patients in each treatment arm provides 80% power to detect an absolute reduction of 30% in the two-year failure rate (biochemical, clinical, or biopsy), from 52.5% to 22.5%, using a one-sided Fisher's exact test with 5% significance level. To ensure a minimum of 72 study patients evaluable for the two year failure rate as our main study endpoint, we plan to enroll a total of 76 patients.

Based on an accrual rate averaging 2 patients per month, we plan to complete enrollment in 3.2 years. Patients will be followed for five years giving total study duration of 8.2 years. Analyses of some secondary endpoints, including acute toxicity, psychosocial parameters, biomarker distribution on ultrasound-guided biopsies, and initial MRI findings may be reported before the efficacy endpoints, including the primary endpoint. These secondary endpoints will be analyzed after all planned patients have been accrued, completed treatment and have a minimal potential follow-up of 3 months from the end of RT. The main efficacy endpoint requires less than five years follow up and will be performed after all patients have been assessed for two year post treatment failure status (2 yr. biopsy). Final efficacy analysis will be at the conclusion of study when patients have been followed for 5.25 years.

14.3 Definitions and endpoints:

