Evaluable: Patients who are study eligible and receive an initial dose of radiotherapy, either SIMRT or HTIMRT will be considered *evaluable for safety*, regardless of whether or not the full course of radiation treatment is completed according to protocol. To be *evaluable for efficacy*, study eligible patients must complete radiation treatment and have follow up sufficient to include either the planned 2-year post treatment biopsy or earlier evidence of biochemical or clinical failure (within 2 years of treatment completion). These patients comprise the main analysis set.

Exclusions: Any patient who is enrolled on study but does not receive an initial dose of radiation treatment will be excluded from all efficacy analyses. Any patient who initiates treatment and is later found to be ineligible for study (e.g., protocol violation) will be withdrawn from study but will be followed for toxicity and clinical outcome; the experience of such patients will be characterized separately from that of patients who are evaluable for efficacy. Reasons for exclusion of enrolled patients from analysis of safety or efficacy will be characterized.

Study endpoints are defined in Section 9.1.

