14.4 Stratification Factors

Patients will be randomized in equal proportion to receive either HTIMRT or SIMRT using a permuted block design stratified by baseline PSA (<10 vs 10 to \leq 100), Gleason score (6-7 vs 8-10) and short term (4 to 6 months) androgen deprivation (STAD) therapy (Y vs. N). Where appropriate, these factors will be used in the analysis of study data; for example, to stratify statistical tests comparing treatment arms or to adjust regression models. We note that STAD therapy will be recommended for all Gleason 8 patients; however, we allow for all eight possible combinations as strata in order to ensure equal treatment allocation in the event that enrollment includes a small number of patients with uncommon combinations of these factors.

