14.5 Analysis plan

The main analysis of study findings will be done by treatment assignment (intention-to-treat) in all patients who meet evaluable criteria as stated in Section 14.3. We will report any instances of treatment crossover. As noted above, analyses of some secondary endpoints, including acute toxicity, psychosocial parameters, tissue and blood product-related biomarker distribution on ultrasound-guided biopsies, and initial MRI findings may be reported before the efficacy endpoints, including the primary endpoint. These secondary endpoints will be analyzed after all planned patients have been accrued, completed treatment and have a minimal potential follow-up of 3 months from the end of RT. An initial analysis of clinical outcome (efficacy) is

planned after all patients have been assessed for two year post treatment failure status and a final analysis will be done at the completion of the planned 5 year follow up of all study patients. Statistical tests comparing treatment arms will be one-sided with 5% significance level and stratified where appropriate by the factors considered in randomization.

Statistical analysis will include descriptive statistics for patient demographics and baseline disease characteristics, both overall and by treatment arm. Counts and percentages will be used to summarize the distribution of categorical variables while median, range, mean and standard deviation will be used for continuous variables. Baseline characteristics will include age, sex, race/ethnicity, T-category, Gleason score, PSA, risk group and performance status. Biomarker measurements and proteomic/genomic profiles obtained from baseline biopsy will also be summarized with descriptive statistics. (76)

Treatment received will be summarized by the type of RT and STAD components of therapy, the number and duration of treatment delays, and the rates of discontinuation or completion. Summaries will be provided for each treatment arm. Safety analysis will include a detailed tabulation of acute and late occurring toxicity by type and grade, both overall and by treatment arm. Additionally, we will estimate the cumulative incidence (from start of treatment) of grade 2+ and 3+ genitourinary (GU) toxicity and of grade 2+ and 3+ gastrointestinal (GI) toxicity in each treatment arm. Death without the toxicity of interest will be treated as a competing risk, and toxicity rates will be compared by treatment arm using Gray's test. (77, 78)

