The primary trial endpoint, two-year failure rate, will be estimated for each treatment arm as a proportion with corresponding 95% confidence interval by the exact binomial method. Comparison of the failure rate for SIMRT versus HTIMRT will be based on a one-sided Fisher's exact test at a 5% significance level. Similar estimation and comparison will be done for the biopsy failure rate among clinical/biochemical failure-free patients at the two year post RT follow up. Biopsy findings two years post RT will be further characterized as negative, atypical, carcinoma with treatment effect, or carcinoma without treatment effect and compared by treatment arm using Fisher's exact test. Biomarker and proteomic/genomic characteristics of prostate biopsy tissue obtained two-year post treatment, and changes relative to baseline, will be summarized by descriptive statistics. Change from baseline will be tested for significance using t-test (means) or McNemar's test (proportions) for paired data and comparison of changes by treatment arm will be based on two-sample tests (t-test or Fisher's exact test). (For biomarker studies, nonparametric tests or data transformations to attain approximate normal distributions will be applied as needed.) Logistic regression models adjusted for treatment will be used to investigate the association between baseline factors, including biomarkers and proteomic/genomic profiles, and biopsy failure two-years post treatment. Changes in biomarkers and proteomic/genomic characteristics will also be investigated for association with biopsy failure. (79)

Patients will be followed for disease progression and vital status for a period of five years after completing study treatment. Progression of disease will be categorized as biochemical failure (BF), clinical failure (CF), or combined (BF + CF), where combined failure refers to documented evidence of BF and CF occurring within 6 months of each other with the earlier date used. CFs will be further categorized as local, nodal, or distant. Start of subsequent therapy will be considered a failure event for selected analyses as indicated in the table below. Deaths will be categorized as related/unrelated to prostate cancer. The number of observed failures will be tabulated by treatment arm and failure type. Similarly, vital status will be tabulated by treatment arm and presence or absence of disease at last follow up.

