APPENDIX I
STUDY CALENDAR

Assessment	Prior to RT	Weekly during RT	Follow-up					Other
			During Last Week of RT	6 Weeks after RT	3 Mo after RT	Every 6 months thereafter up to 2-2.25 years post-end of all treatment	FU until 5-5.25 years (At the discretion of the physician)	
History & Physical Exam*	X	X	X	X	X	X	X	
Functional-MRI of prostate/pelvis ^a	X				X			At 9 mo., and within 2 mo. of 2 yr. prostate biopsy
Bone Scan ^b	X							As needed
Prostate protocol biopsy ^c	X							2 – 2.5 years post completion of all therapy (2 yr. biopsy)
Prostate fiducial markers ^c	X							
CT and MRI simulation	X							
PSA ^a	X		X	X	X	X	X	
Serum-Testosterone ^d	X		X	X	X			At 9 months after RT
Liver function tests ^a	X		X	X	X			
Complete blood cell counts ^a	X		X		X			
Lipid Profile ^a	X		X	X	X			At 9 months and within 2 mo. prior to 2 yr. prostate biopsy
EPIC-SF-12, MAX-PC ^e	X		X	X	X			At 9 months, 15 mo. and yearly to 5.25 years
IPSS ^f	X		X	X	X	X	X	At each follow-up visit
ADT ^g	X							
Plasma and serum, and urine collection for research ^h	X		X		X			Within 2 mo. prior to 2 yr. prostate biopsy

*Toxicity will be assessed at each scheduled history and physical exam visit. Interval history will be obtained during and following RT at these visits. History and physical within 8 weeks prior to protocol entry.

(a)Obtained \leq 3 months of enrollment.

(b)Obtained \leq 4 months of enrollment if PSA >15 ng/mL or Gleason score ≥ 8 disease. For all others, to be obtained at the discretion of the treating physician.

- (c) The initial protocol prostate biopsy is optional per the patient's desire, as indicated on the consent, and will be carried out during fiducial marker placement, if applicable. In follow-up, prostate biopsy will be obtained at the first sign of local failure or a rising PSA, or at 2-2.5 years after treatment (after radiotherapy or androgen deprivation – whichever is longer) if there is no evidence of failure. The second biopsy is not optional (the patient must agree), but the biopsy may be refused later or may not be performed due to a medical contraindication.

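### The primary one-sided Fisher test is valid and correctly sized but conservative; Boschloo's exact test would raise power from 80.3% to 84.4% at 36 per arm with type I error still at or below 5%

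*Combined protocol and SAP*

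**What the plan says.** Section 14.5 fixes the primary comparison of the two-year failure rate: "Comparison of the failure rate for SIMRT versus HTIMRT will be based on a one-sided Fisher's exact test at a 5% significance level". It asks for a similar comparison of the biopsy failure rate among patients free of earlier failure. Section 14.2 bases the sample size on the same test ("using a one-sided Fisher's exact test with 5% significance level"): 36 evaluable patients per arm give 80% power for 52.5% against 22.5%. To secure 72 evaluable patients, "we plan to enroll a total of 76 patients".

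Section 14.3 defines evaluability for efficacy by events after randomisation. Patients must "complete radiation treatment and have follow up sufficient to include either the planned 2-year post treatment biopsy" or show earlier biochemical or clinical failure. Footnote c of Appendix I accepts that "the biopsy may be refused later or may not be performed due to a medical contraindication".

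Two general statements mention stratification. Section 14.4 foresees using the randomisation factors, for example "to stratify statistical tests comparing treatment arms or to adjust regression models". Section 14.5 says that tests between arms will be "stratified where appropriate by the factors considered in randomization". The sentence on the primary test names no strata. The documents do not mention the actual size of the Fisher test or any unconditional exact test.

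**The concern.** Fisher's test conditions on the total number of failures. In a trial of this size the conditional distribution is coarse, so the achieved type I error lies well below the nominal 5%. The unused error rate costs power.

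That matters here because the design only just reaches its target, and does so at an exactly equal split. Evaluability is settled after randomisation, so 36/36 cannot be taken for granted. If power drops below 80%, a true 30-point reduction is more likely to be missed in a trial with no second look at efficacy. A test that uses more of the permitted 5%, with the same guarantee, needs no further patients.

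**Working it through.** **Inputs.** From Section 14.2: SIMRT rate 0.05 + 0.95 × 0.50 = 0.525; HTIMRT rate 0.525 − 0.30 = 0.225; one-sided 5%; 36 evaluable per arm; 76 enrolled.

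**Formulas.** Let x1 and x2 be the failures on SIMRT (n1) and HTIMRT (n2).
- Fisher p(x1, x2) = P(X ≥ x1), with X hypergeometric given x1 + x2 failures among n1 + n2 patients. Reject if p ≤ 0.05.
- Power = sum over rejected tables of Bin(x1; n1, 0.525) × Bin(x2; n2, 0.225).
- Size = maximum over a common rate π in (0, 1) of the same sum with both rates equal to π.
- Boschloo: reject if Fisher's p ≤ c, where c is the largest attainable value for which the size is ≤ 0.05.

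**Step 1: the plan's figure.** Enumerating all 37 × 37 tables at 36/36, Fisher power is 80.28%. The stated 80% reproduces.

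**Step 2: true size of Fisher at 36/36.** The maximum is 3.82%, at π = 0.50. It is 3.80% at 0.525, 3.38% at 0.375 and 2.79% at 0.225.

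**Step 3: Boschloo at 36/36.** c = 0.0718, maximum size 4.82%, power 84.36%. The next attainable cut-off, 0.0744, would have size 5.11%, so it is not admissible. Boschloo rejects every table that Fisher rejects and 18 more. The gain is 84.36 − 80.28 = 4.08 points.

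**Step 4: other evaluable numbers.**

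| SIMRT/HTIMRT | Fisher power % | Boschloo power % |
|---|---|---|
| 33/39 | 78.6 | 84.5 |
| 34/38 | 76.8 | 83.6 |
| 35/37 | 79.8 | 83.2 |
| 36/36 | 80.3 | 84.4 |
| 37/35 | 78.8 | 84.9 |
| 38/34 | 79.4 | 84.1 |
| 39/33 | 78.1 | 82.7 |
| 38/38 | 82.0 | 85.3 |
| 35/35 | 78.5 | 84.2 |
| 34/34 | 76.6 | 82.9 |

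In all of these rows Boschloo's maximum size stays below 5%.

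**Step 5: where the gain arises at 36/36.** Five tables (SIMRT/HTIMRT failures), with their probability under the planned rates in percentage points:

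| Table | 13/6 | 14/7 | 15/8 | 16/9 | 17/10 |
|---|---|---|---|---|---|
| Probability | 0.24 | 0.53 | 0.91 | 1.19 | 1.21 |

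These sum to 4.08, essentially the whole gain. In each, one more HTIMRT failure is allowed than under Fisher. For 17 against 10, Fisher's p is 0.072 and Boschloo's 0.048. Cut-offs also differ at 4, 6, 9–10, 26–30, 32–33 and 35–36 SIMRT failures, but those tables have almost no probability under the planned rates. Cut-offs are identical at 18–25.

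**Step 6: the reserve.** 76 − 72 = 4 patients, and 4/76 = 5.3%. Section 3.3.5 says that the proportion of patients who "withdraw before treatment is about 1-2%. In this trial, the potential for withdrawal is estimated to be 2-3 times higher". That is 2% to 6%, or 1.5 to 4.6 of 76. Enrolment precedes randomisation, so withdrawals after an upgraded biopsy reduce the total without unbalancing the arms. Incomplete radiotherapy or a missing two-year biopsy can do both. The documents give no rate for these losses.

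**The case against.** The strongest reply is that there is no defect. Sections 14.2 and 14.5 agree on test, level and sidedness, the test is valid, and the power is right. Choosing between two valid exact tests is a preference. That stands, and the point is offered only as an improvement. A reader might infer that the trial is underpowered as designed or that its type I error is misstated. The documents support neither.

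Second, the gain is narrow. It sits in tables with an observed difference of 7/36 = 19.4 points and a SIMRT rate of 36% to 47% (13/36 to 17/36). At the expected SIMRT count (0.525 × 36 = 18.9) the two rules coincide. This also stands. The power gain is real, but in most outcomes the decision would be the same.

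Third, timing. Section 14.6 has the research team monitoring clinical outcome continuously, patients know their arm, and they are told their biopsy result. The text is Version 8, dated 03/30/2016. Moving late to a test that rejects more often invites criticism. The documents do not show whether outcomes by arm had been seen, so the change must be conditional.

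Two further inferences are tempting. One is that 33 evaluable patients per arm would now be enough. The equal split gives 81.5% with Boschloo, but 31/35 gives 78.9% (Fisher 78.4%), so it fails once the arms differ. The other is that a stratified test should become primary. Its advantage would depend on stratum sizes and prognostic strengths that the documents do not give.

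Finally, a different test does nothing about bias from analysing only evaluable patients. That is a separate matter.

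**Conclusion.** The plan is sound on this point and can be improved cheaply. At 36/36, replacing Fisher with Boschloo raises power from 80.3% to 84.4% while maximum size goes from 3.8% to 4.8%. With the same 72 patients at 33/39 to 39/33, excluding 36/36, Fisher gives 76.8% to 79.8%, below target at every split, and Boschloo 82.7% to 84.9%.

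These figures rest on the plan's own rates, on independent binomial outcomes in the two arms, and on an unstratified comparison. The amount of post-randomisation loss is unknown, so the uneven splits are a range and not a forecast. The recommendation holds only if no outcome data by arm have been examined.

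**What to change.** Provided that no outcome data by arm have been examined, amend Section 14.5 as follows:

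1. Primary comparison: one-sided 5% Boschloo unconditional exact test on the evaluable patients, with Fisher's p-value as the ordering statistic, maximised over the full range of the common failure rate. Use the same test for the biopsy failure rate.
2. State that the primary test is unstratified, so that the general wording on stratification in Sections 14.4 and 14.5 leaves no choice open.
3. Report the one-sided Fisher test as a sensitivity analysis.
4. Leave the sample size in Section 14.2 as it is, noting that the Fisher basis is conservative.

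If outcomes by arm have been seen, keep Fisher as primary and add only the statement that it is unstratified.

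The cost is one short paragraph, with no new patients, visits or data. The downsides are that the primary test then differs from the one used for sizing, that Boschloo's test is less familiar and needs a little more computation, and that a late change in an open-label trial must be documented as made without knowledge of outcomes by arm.

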- I. No previous history of radical/total prostatectomy (suprapubic prostatectomy is acceptable).
- J. No concurrent, active malignancy, other than non-metastatic skin cancer or early stage chronic lymphocytic leukemia (well-differentiated small cell lymphocytic lymphoma). If a prior malignancy is in remission for ≥ 5 years then the patient is eligible.
- K. Identifiable functional MRI (1.5T or 3.0T MRI) tumor lesion or lesions, that total in volume $<33\%$ of the prostate within 3 months prior to enrollment.
- L. Ability to understand and the willingness to sign a written informed consent document
- M. Zubrod performance status <2 . (Karnofsky or ECOG performance status may be used to estimate Zubrod) See Appendix IV
- N. Willingness to fill out quality of life/psychosocial forms.
- O. Age ≥ 35 and ≤ 85 years.
- P. Serum testosterone is within 40% of normal assay limits (e.g., $x=0.4^*\text{lower assay limit}$ and $x=0.4^*\text{upper assay limit} + \text{upper assay limit}$), taken within 4 months of enrollment. Patients whom have been started on ADT prior to signing consent are not required to have a serum testosterone at this level prior to signing consent; but, a serum testosterone prior to fiducial marker placement is recommended.
- Q. Serum LFTs, taken within 3 months of enrollment.
- R. Complete blood counts, taken within 3 months of enrollment.

4. **Prior to Treatment**

- A. Transrectal research prostate biopsies and gold seed fiducial marker placement, if applicable:
 - a. The pre-RT prostate biopsy is optional for the patient, while the fiducial marker placement is not. For the prostate biopsies, up to a maximum of 14 cores will be taken prior to fiducial marker placement. The number of biopsy cores taken would be up to the discretion of the urologist in conjunction with the team, and

does not have to be defined prior to biopsy if the patient agrees to undergo the procedure.

- b. Ultrasound-guidance is standard for prostate biopsies. The Eigen Artemis® system may be used to fine tune the biopsy locations within the prostate using software to fuse the multiparametric MRI to the ultrasound in real time as the ultrasound is acquiring the images. In addition, these biopsies may be obtained on an MRI directly using established techniques.
- c. 3-4 gold seeds placed in prostate (4 preferred)

B. MRI-simulation: Limited study without contrast at least 1 week after gold fiducial placement.

C. CT-simulation and planning.

5. Treatment Technique

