9.1 Definitions

- *Biopsy failure rate*: The proportion of positive biopsy findings among patients without clinical or biochemical failure 2-2.5 years after completing study treatment (RT or ADT, whichever is longer).
- *Two-year failure rate*: The proportion of patients with either (i) biopsy failure 2-2.5 year after completing treatment (RT or ADT, whichever is longer) or (ii) evidence of biochemical and/or clinical failure (local, regional or distant failure) at any time prior to the planned 2 year post treatment biopsy.
- *Acute toxicity*: toxicity occurring during treatment and within three months of completing treatment
- *Late toxicity*: toxicity occurring more than three months after treatment completion.
- *Failure rate*: The cumulative incidence of biochemical or clinical failure allowing for competing risk as needed. Clinical failure is defined as at least local failure due to newly identified extension outside of the prostate after initial regression, or urinary obstructive symptoms with carcinoma found at TURP or regional/distant failure due to radiographic evidence metastasis (nodal or hematogenous spread). Biochemical failure is defined as $PSA \geq \text{nadir} + 2 \text{ ng/mL}$
- *Failure-free Survival (FFS)*: The elapsed time from start of radiotherapy to first documented evidence of biochemical or clinical failure or death from any cause, whichever occurs first. In the absence of any event defining failure, follow-up time will be censored at the date of last documented failure-free status.

- *Overall Survival (OS)*: The elapsed time from start of radiotherapy to death from any cause. For surviving patients, follow-up will be censored at the date of last contact.
- *Biomarker expression*: Quantification of the amount of the biomarker specific immunohistochemical staining in the area of tumor
- *QOL*: Two contemporary instruments will be utilized to assess patient function and bother (Expanded Prostate Cancer Index Composite-SF12 (EPIC-SF12) and the prostate cancer-specific anxiety Memorial Anxiety Scale for Prostate Cancer patients (MAX-PC).

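### Change in an immunohistochemical tissue marker exists only in men with residual tumor, so its link to biopsy failure likely cannot be estimated and its between-arm test is not a randomized comparison

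*Combined protocol and SAP*

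**What the plan says.** Section 9.1 defines biomarker expression as "Quantification of the amount of the biomarker specific immunohistochemical staining in the area of tumor". It defines the biopsy failure rate as "The proportion of positive biopsy findings among patients without clinical or biochemical failure 2-2.5 years after completing study treatment". Section 14.3 makes these definitions govern the analysis: "Study endpoints are defined in Section 9.1".

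Section 14.5 then plans three uses of tissue from the 2-year biopsy:

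- Description: "Biomarker and proteomic/genomic characteristics of prostate biopsy tissue obtained two-year post treatment, and changes relative to baseline, will be summarized by descriptive statistics". Paired tests of the change are also planned.
- Arm comparison: "comparison of changes by treatment arm will be based on two-sample tests (t-test or Fisher's exact test".
- Association with outcome: "Changes in biomarkers and proteomic/genomic characteristics will also be investigated for association with biopsy failure". No model is named for this step; the preceding sentence uses logistic regression for baseline factors.

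The same section grades the 2-year biopsy as "negative, atypical, carcinoma with treatment effect, or carcinoma without treatment effect" but does not say which grades count as positive. On the baseline side, item 4 of the synopsis states: "The pre-RT prostate biopsy is optional for the patient". No section says what value a man with tumor-free 2-year tissue receives, restricts these analyses to a subset, or names another tissue compartment for the staining.

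**The concern.** A marker defined by staining within tumor has no value where there is no tumor. Its change from baseline to 2 years is therefore available only in men whose tumor persisted. Two of the planned analyses run into this.

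First, biopsy failure is itself the finding of tumor at 2 years. If the explanatory variable exists only when the outcome has occurred, there is no comparison group of non-failures.

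Second, comparing change between arms among men with persistent tumor conditions on something that happens after randomization and that the boost is intended to alter. The HTIMRT tumors that persist have survived a higher dose and may differ from the larger SIMRT group for that reason alone. A significant difference could be misread as a biological effect of HTIMRT on the marker.

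**Working it through.** **Planning figures (Section 14.2).** There are 36 evaluable men per arm, with a two-year failure rate of 52.5% under SIMRT and 22.5% under HTIMRT, tested by one-sided Fisher's exact test at 5% for 80% power. The SIMRT rate reproduces: 0.05 + 0.95 × 0.50 = 0.525. Exact enumeration gives power 0.803 at 36 per arm (0.785 at 35), so the stated 80% reproduces. The plan gives no sample size or power for the biomarker-change analyses.

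**Who can have a change value, if any residual carcinoma counts as positive.**

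- SIMRT: 36 × 0.95 × 0.50 = 17.1 men.
- HTIMRT: 36 × (0.225 − e), where e is the early biochemical or clinical failure rate. The plan does not give e for this arm. For e = 5%, 2.5% and 0% the result is 6.3, 7.2 and 8.1 men.
- Total: 17.1 + 6.3 = 23.4 to 17.1 + 8.1 = 25.2 of 72.
- Expected non-failures: 72 − 36 × 0.525 − 36 × 0.225 = 72 − 18.9 − 8.1 = 45.0. None of them has a change value.

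The association would thus rest on about 23 to 25 failures and no non-failures. Scoring tumor-free men as zero staining does not rescue it, because that writes the outcome into the predictor.

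**Early failures.** Section 8.0 plans the 2-year biopsy in men with or without documented failure. At 5%, that is 0.05 × 36 = 1.8 men per arm who might add tumor tissue. They lie outside the biopsy-failure denominator and supply no non-failures.

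**Paired baseline.** If the baseline is the optional research biopsy, the pairs fall with uptake. The plan gives no uptake figure. Assuming 75%, 50% or 25%, with e = 5%:

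| Uptake | SIMRT | HTIMRT | Total |
|---|---|---|---|
| 75% | 12.8 | 4.7 | 17.5 |
| 50% | 8.5 | 3.1 | 11.7 |
| 25% | 4.3 | 1.6 | 5.8 |

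**What the arm test could detect.** At one-sided 5% and 80% power (noncentral t), 17 against 6 men detects a difference of about 1.22 SD. With 36 against 36 it would be 0.59 SD.

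**Size of the selection effect (illustration only).** Assume no treatment effect on the marker, tumor persistence of 50% under SIMRT and 0.175 / 0.95 = 18.4% under HTIMRT, and a marker change correlated with latent radioresistance. Simulation at 17 against 6 men gives:

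| Assumed correlation | Spurious arm difference | One-sided rejection rate (nominal 5%) |
|---|---|---|
| 0.3 | 0.20 SD | 11% |
| 0.5 | 0.32 SD | 18% |
| 0.7 | 0.45 SD | 29% |

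The correlations are assumptions; the documents give none.

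**The case against.** Four counter-arguments have force.

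*The sentence on association is not limited to tissue.* A reader might infer that the whole change-against-failure analysis is impossible. The documents do not support that. Section 4.10 collects serum, plasma and urine on a schedule that does not depend on the biopsy result, and Section 2.2 relates circulating DNA and tumor cells to biopsy positivity. Those changes can be analyzed in all sampled men.

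*The restriction to tumor covers staining only.* A reader might extend it to every tissue measure. Section 14.5 also lists proteomic and genomic characteristics of biopsy tissue, and Section 9.1 does not confine those to tumor. The problem is not shown for them.

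*Positive is undefined.* If carcinoma with treatment effect were not counted as positive, some non-failures would have tumor tissue and a model could be fitted. Section 8.0 does discuss treatment-effect cells as a separate situation. The other reading is likelier: Section 1.4.2 describes the earlier rate of nearly 50% in terms of residual tumor cells, and Section 8.0 treats any biopsy containing tumor cells as a result to discuss and manage. The claim about the association has to carry this condition. The claim about the arm comparison does not, since men who cleared their tumor have no value on either reading.

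*The arm comparison can be computed and may be descriptive.* This stands. It would also go too far to say that any difference must come entirely from selection; a treatment effect on the marker and selection by persistence could both contribute, and the test cannot separate them.

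These analyses are also secondary or exploratory. The tissue objective in Section 2.2 compares MRI-suspicious with unsuspicious regions and is untouched.

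**Conclusion.** The point holds for immunohistochemical tissue markers. Under the definition in Section 9.1, their change to the 2-year biopsy exists only in men with residual tumor. If any residual carcinoma is a positive biopsy, the association of that change with biopsy failure is not estimable, because none of the roughly 45 expected non-failures has a value. On either reading of positive, the between-arm comparison is not a randomized one.

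On the first reading, the set is about 17 SIMRT against 6 to 8 HTIMRT men, resting on the planning rates and an HTIMRT early-failure rate of 0 to 5%. It grows slightly with biopsied early failures and shrinks if the optional biopsy is the baseline. The primary endpoint, its sample size, and the use of baseline tissue markers as predictors are unaffected. The change is worth making, but it is a repair to secondary analyses.

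**What to change.** Amend Section 14.5 as follows.

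1. For immunohistochemical tissue markers, relate biopsy failure to baseline values only.
2. Keep the analysis of change against biopsy failure for blood and urine markers drawn before the biopsy. Keep it for tissue proteomic and genomic measures only where they can be measured in tumor-free tissue.
3. Report change in immunohistochemical tissue markers descriptively, in men with paired tumor tissue, with counts by arm. Drop its between-arm significance test, or label that test exploratory and non-randomized.

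Stating which of the four biopsy grades count as positive would settle the condition attached to the first conclusion. If the sponsor wants a staining measure in every man, it would need to define a compartment that can be read without tumor.

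The cost is wording only. What is given up is at most one exploratory between-arm test on few men.
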